#### **9.3.4. Analysis of secondary outcomes**

Secondary outcomes (EQ5, CCQ, changes in lung function, BODE index) will be analyzed using analysis of covariance (ANCOVA), once assumptions for the convenience of this analysis are confirmed, with baseline values and potential confounding factors as covariates and study group as independent variable (Miller, G. A., & Chapman, J. P. 2001). After, Least square (LS) mean  $\pm$  standard error (SE) will be calculated for variables involving each outcome.

Baseline differences between study groups (controlled and uncontrolled COPD patients) will be performed using the Chi-square test (exact Fisher test with observed frequencies  $< 5$ ) for categorical variables whereas continuous variables were tested using *t* test (U-Mann Whitney test if the variables were not normally distributed). A stepwise multivariate logistic regression model to predict control in COPD patients will be performed. All variables explored in the univariate analyses will be considered in the multivariate model as covariates. A conservative significance threshold of 0.01 was used to determine the qualification of data for entry into or deletion from the model.

Finally, an analysis will be performed to evaluate the cost-utility of patients with controlled (as compared to poorly controlled) COPD using analysis of covariance. Data will be collected from the economic department of each collaborating center.

All tests were two-tailed, and significance was set at 5%. All analyses will be carried out using SPSS version 20, SAS version 9.3 and Microsoft Office EXCEL 2007.

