#### **4.5. SAMPLE SIZE CALCULATION**

Based on a previous pilot study in Spain, approximately 55% of patients with COPD are controlled based on the proposed criteria. The sample size has to be calculated in order to have enough sample of both subgroups (controlled/non controlled) in both levels of severity (mild to moderate and severe to very severe) that will allow to identify differences in outcomes (main outcome: difference in annualised rate of composite outcome). Since there is not previous information about the frequency of the composite outcome, we have performed a conservative approach using the expected frequency of exacerbations in the sample calculation. According to results from ECLIPSE Study, annualised rate of exacerbations in COPD patients in entire sample was 1.2 per person (15). We hypothesize that, in controlled COPD patients, this annual rate can be 40% lower (0.72 per person). Accepting an alpha risk of 5% and a beta risk of 10% in a two-sided test, a total of 285 COPD patients will be necessary to find this annualised incidence ratio difference as statistically significant. It is expected that two thirds of controlled patients have mild to moderate COPD and one third of these have severe to very severe COPD. With an expected drop-out rate of 15%, a total of 328 patients will be enrolled in the study. Sample size has been calculated with !NI2IS macro (SPSS V20).

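### Protocol 9.3.4 switches to Fisher's exact test on observed rather than expected counts below 5, so the data pick the test, at a small cost in power

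*Protocol*

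**What the plan says.** Protocol section 9.3.4 compares the two control groups at baseline. For categorical variables, the comparison "will be performed using the Chi-square test (exact Fisher test with observed frequencies" below 5). Expected frequencies are not mentioned, and nothing is said about a continuity correction. The section closes with the general rule "All tests were two-tailed, and significance was set at 5" per cent.

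The same section then describes a stepwise logistic model for control status and states: "All variables explored in the univariate analyses will be considered in the multivariate model as covariates". Its 0.01 threshold governs entry into and removal from that model.

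The group sizes follow from section 4.5: "approximately 55% of patients with COPD are controlled based on the proposed criteria", "a total of 285 COPD patients will be necessary", and, after allowing for drop-out, "a total of 328 patients will be enrolled in the study".

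**The concern.** Pearson's chi-square statistic is referred to a continuous distribution. That approximation is poor when expected cell counts are small, and expected counts depend only on the table's margins. Observed cells also carry the difference under test. If a characteristic is moderately uncommon and really differs between the groups, one observed cell will often be below 5 while every expected count is above 5. The written rule then discards a valid chi-square test because of the result.

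At stake are the univariate comparisons of categorical characteristics listed in section 9.3.1 (comorbidities, medications, occupation, smoking status). They bear on secondary objective 3 and secondary outcome 6, the characteristics associated with control. Uncommon comorbidities or individual drugs are where the rule would act. The protocol fixes this rule explicitly, so it is a misstated rule and not a detail left to a later analysis plan.

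**Working it through.** The protocol derives no figure from this rule, so there is none to reproduce. The check asks how often the rule departs from the expected-count rule, and with what effect.

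**Inputs.** The controlled share is 55% (section 4.5). Three totals are used:
- 285, the required number: 157 v 128.
- 328, the number enrolled: 180 v 148.
- 279, a low case that is not in the protocol: 328 × 0.85 = 278.8, split 153 v 126.

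The level is 5%, two-sided. Prevalences are assumptions, because the protocol gives none. Chi-square is uncorrected Pearson unless stated otherwise.

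**When expected counts are adequate.** The smallest expected count is (number with the characteristic) × (smaller group) / N. At 157 v 128, 12 × 128 / 285 = 5.39 and 11 × 128 / 285 = 4.94. From 12 patients upward, all expected counts therefore reach 5.

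**One table.** Take 4 of 157 v 10 of 128. The smallest expected count is 14 × 128 / 285 = 6.29, so chi-square is adequate. X² = N(ad − bc)² / (product of the margins) = 285 × (4 × 118 − 153 × 10)² / (157 × 128 × 14 × 271) = 4.18, p = 0.041. One observed count is 4, so the written rule uses Fisher's test, p = 0.053.

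**All tables with up to 39 carriers per group.** At each of the three sizes, the written rule uses Fisher's test in 300 tables where every expected count is at least 5. Four of these lose significance at 5% (4 v 10, 10 v 2, 12 v 3, 14 v 4) and none gains it. In three tables (5 v 5, 5 v 6, 6 v 5) the rule errs the other way: an expected count is below 5 but chi-square is kept. Those p-values all exceed 0.5, so this is harmless.

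**Size and power.** Each is the sum, over all tables (a, b), of Bin(a; n₁, p₁) × Bin(b; n₂, p₂) × [p-value ≤ 0.05]. Fisher's test is used if any observed count is below 5 (written rule) or if any expected count is below 5 (usual rule).

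| Prevalence, controlled v uncontrolled | N | Written rule | Expected rule |
|---|---|---|---|
| 3% v 3% (size) | 279 / 285 / 328 | 3.5 / 3.6 / 3.7% | 3.8 / 3.9 / 4.2% |
| 5% v 5% (size) | 279 / 285 / 328 | 3.7 / 4.0 / 4.0% | 4.8 / 5.1 / 4.9% |
| 10% v 10% (size) | 279 / 285 / 328 | 4.9 / 4.9 / 4.9% | 5.0 / 4.9 / 4.9% |
| 2% v 8% (power) | 279 / 285 / 328 | 63.1 / 64.8 / 71.2% | 65.4 / 67.1 / 73.3% |
| 8% v 2% (power) | 279 / 285 / 328 | 58.6 / 60.4 / 67.8% | 65.1 / 66.8 / 73.0% |

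**Dependence on the result.** With no group difference, the written rule displaces an adequate chi-square in at most about 12% of samples (prevalence 4% to 5%), and in under 0.5% at 10% prevalence. At N = 279 the share is 49% for 2% v 8% and 70% for 8% v 2%.

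**Continuity correction.** If the chi-square were corrected, the direction reverses. At N = 279 the written rule has power 61.5% against 58.6% (2% v 8%) and 58.1% against 51.6% (8% v 2%). For 4 v 10 at 157 v 128, the corrected chi-square p is 0.077 against Fisher's 0.053.

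**The case against.** The best defence is that both tests are acceptable and little depends on the choice. Much of that stands. Fisher's test holds its error rate at or below 5%, and the size of the written rule stayed at or below 5% in every null case run. All explored variables go forward to the multivariable model whatever their univariate p-values. The primary composite is analysed by Mann-Whitney and logistic regression (section 9.3.3), and the listed secondary measures by analysis of covariance (section 9.3.4).

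A reader might infer more than the documents support:

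- **That the resulting p-values are generally too large.** They are not. At 157 v 128, Fisher's p is below the uncorrected chi-square p in 230 of the 300 tables, mostly ones already far below 0.05 (12 v 0: 0.0007 against 0.0014). The conservatism is a matter of the 5% boundary.
- **That the effect always runs one way.** This holds for decisions at 5% with uncorrected chi-square. It fails with a continuity correction, which the protocol neither requires nor excludes.
- **That the rule fails a 5% level which the alternative would deliver.** At 2% prevalence and N = 279, both rules have size 2.8%.
- **That losses should also be counted at the 1% level.** The 0.01 threshold belongs to the stepwise model, not to these tests.
- **That overriding chi-square in 49% of samples means 49% of conclusions change.** At 2% v 8% and N = 279, power differs by only about 2.3 points.

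None of this is a reason to write observed instead of expected.

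**Conclusion.** The trigger in section 9.3.4 names the wrong quantity, and the test used comes to depend on the result. With uncorrected Pearson chi-square, and characteristics present in roughly 3% to 8% of patients, the consequence is mild conservatism. Size drops from about 5% to about 4% where the effect is largest, near 5% prevalence. Power drops by about 2 points when the characteristic is rarer among controlled patients (2% v 8%) and by 5 to 7 points in the mirror case (8% v 2%). Outside that band the two rules nearly coincide.

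Type I error is not inflated. The primary outcome, the sample size and the candidate list for the stepwise model are unaffected. The figures rest on the assumed prevalences, the 55/45 split and the absence of a continuity correction. This is a wording correction of low severity.

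**What to change.** In section 9.3.4, make the exception apply when any expected frequency is below 5, and state that uncorrected Pearson chi-square is used otherwise. The second part matters because the direction of the effect depends on it.

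The cost is one word and one short phrase, with no new data and no change to sample size. One small consequence should be accepted knowingly: uncorrected chi-square can exceed 5% by a fraction of a point (5.1% at 5% prevalence and N = 285 in the table above), which is of no practical importance for these comparisons.

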## Definition of COPD Control

Control of COPD is defined as a composite of low disease impact, adapted to the patients' level of COPD severity, and clinical stability over time.

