#### **4.3.2. Secondary outcomes**

The secondary outcome for the study will be:

- 1) The (annualized) rate of exacerbations in patients controlled and uncontrolled at baseline
- 2) Time to the first composite event in patients controlled and uncontrolled at baseline
- 3) Time to the first exacerbations in patients controlled and uncontrolled at baseline
- 4) Comparison of CAT and CCQ as tools to identify impact and stability in COPD (i.e. a comparison of their scores' alignment with other relevant scores over the 24-month follow up period).
- 5) Distribution of control level across in those receiving guideline vs non-guideline recommended therapy (i.e. stratification of control across different treatment groups)
- 6) Demographic and clinical characteristics associated with poor control of COPD (i.e. comparison of control status across different demographic groups).

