### 9.3. Statistical analysis

Baseline and outcome variables will be analysed as a complete dataset and by treatment groups (split by baseline COPD severity).

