#### 9.3.1. *Baseline variables*

Baseline variables will include:

- Demographics and lifestyle:
  - Sex
  - Age

- Height, weight, BMI
- Occupation
- Impact:
  - Dysnea (mMRC score)
  - Sputum presence; sputum colour
  - Daily physical activity (minutes walked / day)
  - CAT
  - CCQ
  - Impact at time of assessment (High vs Low)
- Stability
  - Exacerbations in the last 3 months (patient-reported and based on clinical records)
  - Change in CAT and CCQ in the last 3 months (where available)
  - Stable (vs unstable) disease at time of assessment (Y/N)
- COPD Control Status:
  - Controlled
  - Poorly controlled
- Comorbidities
- COPD medications (and cost)
- Other concomitant medications (and cost)
- Lung function (FEV1, FVC, FEV1/FVC)
- BODE Index
- Smoking Status
  - History (pack years)
  - Current status

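### The model for predictors of control ignores severity class, although the low-impact limits loosen at BODE/Ex 5; pooled associations with severity markers are biased towards the null and can change sign.

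*Protocol*

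**What the plan says.** The Definition of COPD Control begins: "Control of COPD is defined as a composite of low disease impact". It goes on to say that impact is adapted to severity. The class-specific lists and Table 3 give these low-impact limits:

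| Item | BODE/Ex 4 or less | BODE/Ex 5 or more |
|---|---|---|
| CAT | 10 or less | 20 or less |
| CCQ | 1 or less | 2 or less |
| mMRC | 0-1 | 0-2 |
| Rescue use | at most 3 times in the last week | at most 2 times a day |

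The clinical items and the questionnaires are alternative routes to low impact. Table 3 also loosens walking time, from 60 to 30 minutes, while the list for severe disease keeps 60.

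The COPD Severity paragraph of section 4.4.1.3 builds BODEx from BMI, obstruction, dyspnoea and exacerbations.

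Secondary outcome 6 in section 4.3.2 reads: "Demographic and clinical characteristics associated with poor control of COPD (i.e. comparison of control status across different demographic groups"). Section 9.3.4 serves it as follows: "A stepwise multivariate logistic regression model to predict control in COPD patients will be performed". It adds: "All variables explored in the univariate analyses will be considered in the multivariate model as covariates". Entry and removal are set at 0.01. The baseline list in section 9.3.1 contains lung function, BMI, BODE Index, CAT, CCQ and mMRC.

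The only severity split is the opening line of section 9.3. It analyses variables as a complete dataset and "by treatment groups (split by baseline COPD severity").

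**The concern.** The dependent variable changes its yardstick at BODE/Ex 5, and the candidate predictors help decide which yardstick a patient gets. Lower FEV1 makes a patient more likely to be symptomatic, which lowers the chance of control. It also makes the patient more likely to be judged against the looser limit, which raises that chance. A pooled coefficient adds these opposing effects.

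Secondary objective 3 asks which characteristics go with control, with a view to targeting patients. For that purpose only the first effect is of interest. A pooled model would understate the association of severity markers with poor control, could miss it, or in some settings could report it the wrong way round.

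**Working it through.** The protocol states no figure for this model, so there is none to reproduce. It gives no CAT distribution, no FEV1 distribution and no severe share for the cohort. The checks below therefore show ranges over assumptions.

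**1. What the sample-size section implies.** Section 4.5 expects 55% controlled, two thirds of them mild to moderate. With m the mild/moderate share of the cohort:

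- P(control | mild) = 0.55 × (2/3) / m
- P(control | severe) = 0.55 × (1/3) / (1 − m)

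| m | Mild | Severe | Odds ratio, severe vs mild |
|---|---|---|---|
| 60% | 61.1% | 45.8% | 0.54 |
| 66.7% | 55.0% | 55.0% | 1.00 |
| 70% | 52.4% | 61.1% | 1.43 |
| 75% | 48.9% | 73.3% | 2.88 |

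On the protocol's own expectations, the severe class is the better controlled one only if it is less than a third of the cohort. That share is not stated.

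**2. The limit alone, on the CAT route.** Assume CAT is normal with SD σ, mean μ in the mild class and μ + d in the severe class:

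- P(low | mild) = Φ((10.5 − μ)/σ)
- P(low | severe) = Φ((20.5 − μ − d)/σ)

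With σ = 7 and μ = 14, the mild value is Φ(−0.5) = 31%. At d = 6 the severe value is Φ(0.5/7) = 53%, odds ratio 2.5. At d = 10 both are 31%, odds ratio 1.0. At d = 12 the odds ratio is 0.6. The limits differ by 10 points, so the severe class reaches low impact more often whenever its mean CAT is less than 10 points higher, whatever μ and σ.

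**3. Effect on the FEV1 coefficient.** Simulation with N = 328 and 400 runs per setting. Assumptions:

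- FEV1 has mean 52 and SD 17.
- The severity score falls with FEV1, with noise; about 17% of patients are severe.
- CAT has mean 13 at FEV1 52, with residual SD 6.5.
- Control is low impact by CAT plus stability (75% of mild, 65% of severe patients).

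The table gives odds ratios for control per 10 points worse FEV1. Below 1 is the expected direction.

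| CAT points worse per 10-point FEV1 fall | Pooled | Pooled, CAT in model | Within mild | Within severe | One CAT limit of 10 for all, pooled |
|---|---|---|---|---|---|
| 0 | 1.19 | 1.31 | 1.00 | 0.99 | 0.98 |
| 0.5 | 1.09 | 1.32 | 0.90 | 0.96 | 0.88 |
| 1 | 1.00 | 1.34 | 0.81 | 0.89 | 0.79 |
| 1.5 | 0.91 | 1.33 | 0.73 | 0.82 | 0.71 |
| 2 | 0.83 | 1.34 | 0.66 | 0.75 | 0.64 |
| 3 | 0.70 | 1.34 | 0.56 | 0.60 | 0.54 |

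- The pooled value lies above both within-class values in every row. The single-limit column does not show this, so the cause is the switch of limit.
- Without CAT, the pooled estimate passed p < 0.01 in the wrong direction in 41% of runs in the first row, 11% in the second and none from the third on.
- With CAT in the model, it did so in 46% to 69% of runs. A patient with CAT 11-20 meets the CAT limit only if classed as severe, so at a given CAT score worse FEV1 raises the chance of control.

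**4. Effect of the severe share.** A second set-up models low impact by CAT only: FEV1 55 ± 17, CAT = 12 + s × BODEx, SD 7. Odds ratios per 10 points worse FEV1, for s = 0.5, 1, 1.5, 2:

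- 28% severe: pooled 1.29, 1.19, 1.07, 0.96; class-adjusted 0.94, 0.88, 0.82, 0.78.
- 19% severe: pooled 1.20, 1.10, 1.01, 0.91; class-adjusted 0.93, 0.87, 0.82, 0.77.

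A third run, with 6% to 28% severe and a stability component, gave 0.83 to 1.30 pooled and 1.02 to 1.34 class-adjusted per 10 points better FEV1. Inverted to the direction used above, that is 1/1.30 = 0.77 to 1/0.83 = 1.20 pooled, and 1/1.34 = 0.75 to 1/1.02 = 0.98 class-adjusted.

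**The case against.** **Section 9.3 already splits by severity.** Its opening line heads the whole section, and in a study without treatment arms its treatment groups may well mean the controlled and uncontrolled groups. That reading is possible. But the line does not name this model and keeps the complete-dataset analysis. Section 9.3.4 then fixes the method, the candidate rule and the threshold without a severity term. A later analysis plan could settle the matter, but the text as fixed does not.

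**BODE Index is already a candidate.** This stands in part. With linear BODEx in the model, the FEV1 odds ratio per 10 points better was near null (0.93 to 1.04) in the third run, so a clear FEV1 reversal is not to be expected there. Part of the artefact moves to the BODEx term instead. Selection at 0.01 need not keep BODE Index, and a linear term does not capture a step at 5.

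**The adaptation is deliberate.** This stands. The definition is not the complaint, and a pooled model does describe who counts as controlled. It does not separate the patient's state from the limit applied, which the objective needs.

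**A stronger reading.** A reader might infer that markers of worse disease will look protective and that advice on targeting will be wrong. The documents do not support that:

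- Reversal needs a shallow CAT-severity slope, a larger severe share, or CAT or CCQ left in the model.
- A cohort with mostly severe patients would show a larger artefact but fits section 4.5 badly. At 60% severe, that section implies control in 0.367/0.40 = 92% of mild and 0.183/0.60 = 31% of severe patients.
- The CAT-only calculations leave out the clinical route to low impact. Stability is also required for control, and severe patients may fail it more often.
- Effects on age, comorbidity or treatment intensity were not examined.

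**Conclusion.** The point holds as a bias in a secondary analysis. One unstratified model of a severity-adapted outcome gives associations with FEV1 and similar markers that are pulled towards the null, and sometimes past it. In the main simulation, the pooled odds ratio per 10 points worse FEV1 was 0.70 to 1.19, where the within-class values were 0.56 to 1.00.

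The direction of the bias follows from the definition and was the same in every setting tried. Its size, and whether the sign changes, rest on assumed CAT and FEV1 distributions and on an assumed severe share. The main simulation also gave 31% to 33% controlled, below the 55% the protocol expects, so its figures illustrate the problem and do not forecast the result. The primary comparison is not affected by this point. The change is worth making because it is nearly free.

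**What to change.** In section 9.3.4, and for secondary outcome 6:

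- Force baseline severity class (BODE/Ex 0-4 versus 5 or more) into the model outside the stepwise selection, or fit the model separately by class.
- Check the class-by-FEV1 interaction.
- Report associations with control as class-adjusted or within class.
- Reword the severity split in section 9.3 so that it names the groups that exist and says that it covers this model.
- Align the severe-class column headings of Tables 1 to 3, which say above 5, with the lists, which say 5 or more, so that a score of 5 has a class.

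Forcing in class does not settle whether CAT, CCQ and mMRC, which define the outcome, belong among the candidates. The plan should say that they are left out.

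The cost is a wording change with no new data, and somewhat wider intervals, mainly in the smaller class.

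### The candidate rule in section 9.3.4 admits the items that define COPD control into the stepwise model that predicts control, so the adjusted model is circular

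*Protocol*

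**What the plan says.** **The model.** Section 9.3.4 states: "A stepwise multivariate logistic regression model to predict control in COPD patients will be performed". It serves the third secondary objective (section 2.3) and the sixth secondary outcome (section 4.3.2), both about demographic and clinical characteristics associated with control status.

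**The candidates.** The next sentence reads: "All variables explored in the univariate analyses will be considered in the multivariate model as covariates". The sentence before the model shows which univariate analyses are meant: "Baseline differences between study groups (controlled and uncontrolled COPD patients) will be performed using the Chi-square test", with t or Mann-Whitney tests for continuous variables. Entry and removal are governed by a single threshold: "A conservative significance threshold of 0.01 was used to determine the qualification of data for entry into or deletion from the model".

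**The baseline variables.** Section 9.3.1 is the only list of them. Under impact it has mMRC, sputum, walking time, CAT, CCQ and the derived class "Impact at time of assessment (High vs Low"). Under stability it has "Exacerbations in the last 3 months (patient-reported and based on clinical records"), change in CAT and CCQ, and the derived class "Stable (vs unstable) disease at time of assessment (Y/N"). It also lists COPD control status and the BODE index.

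**The outcome of the model.** The definitions chapter says: "Control of COPD is defined as a composite of low disease impact", adapted to severity, together with clinical stability over time. Section 4.4.2 assigns patients to the controlled or uncontrolled group at the baseline visit, month 3.

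**The concern.** A model meant to find out who is controlled should be offered characteristics that could, in principle, be unrelated to control. Here the rule offers the model the ingredients of its own dependent variable, measured at the same assessment. Whatever it selects from those ingredients restates the definition.

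At stake is the only multivariable analysis for this objective. A reader would take the selected variables as correlates of control, and the absence of age, comorbidity, smoking or lung function as evidence that they do not matter. Neither conclusion would be warranted.

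**Working it through.** The plan states no figure here to reproduce. The check compares lists, follows the logic of the definition, and adds an illustration on assumed data.

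**Step 1. Definition against candidate list** (Tables 1 to 3 of the definitions chapter; section 9.3.1)

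| Part of the control definition | In the 9.3.1 list? |
|---|---|
| mMRC | yes |
| Rescue medication use | no |
| Walking time per day | yes |
| Sputum | yes |
| CAT | yes |
| CCQ | yes |
| Exacerbations, last 3 months | yes |
| Change in CAT | yes |
| Change in CCQ | yes |
| Impact class (derived) | yes |
| Stability class (derived) | yes |
| Severity, which sets the cut-offs | yes (BODE index) |
| Control status (the outcome) | yes |

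Of the nine raw items, eight are listed (9 − 1 = 8). No section excludes any of them from the candidates.

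**Step 2. Both derived classes offered.** Let L = 1 for low impact and S = 1 for stable, so control Y = L × S. Take the linear predictor b(L + S − 1.5):

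- L = S = 1 (controlled): b(2 − 1.5) = +0.5b
- exactly one equals 1 (uncontrolled): b(1 − 1.5) = −0.5b
- L = S = 0 (uncontrolled): b(0 − 1.5) = −1.5b

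For any b > 0, every controlled patient lies above zero and every uncontrolled patient below. The likelihood rises towards 1 as b grows and never reaches a maximum. Separation is complete, finite estimates do not exist, and the AUC is 1.00. This follows from the definition alone.

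**Step 3. Raw items only.** Tables 2 and 3 require no exacerbation in the 3-month window, so every controlled patient has a count of zero. The cell for controlled patients with at least one exacerbation is empty, and the coefficient of that single item has no finite estimate (quasi-complete separation). The other raw items need not separate control as linear terms, because the definition allows a clinical-items route or a questionnaire route and uses severity-specific cut-offs.

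**Step 4. Illustration.** This used 100 simulated data sets of 328 patients (the planned enrolment, section 4.5), with forward selection by likelihood-ratio test at p < 0.01. All distributions are assumed. Control was simplified to CAT ≤ 10, no exacerbation and CAT change < 2, without severity strata, CCQ or the clinical-items route. Age, smoking, comorbidity and FEV1 were given true effects. Mean prevalence of control was 41%, against about 55% in the pilot cited in section 4.5.

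| Candidates offered | Runs of 100 selecting each variable | Mean AUC |
|---|---|---|
| Non-defining variables only | FEV1 100, age 71, comorbidity 55, smoking 27 | 0.71 |
| Plus raw items | CAT 100, exacerbations 100, CAT change 100; age 2, smoking 2, FEV1 1, comorbidity 0 | 0.97 |
| Plus impact and stability classes | these two in all 100, nothing else | 1.00 |

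The 0.01 threshold gave no protection, because the defining items have the strongest associations with control.

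**The case against.** **The rule does not cite section 9.3.1.** True, and because that list includes control status it cannot be a literal candidate list; it may be an inventory. The objective speaks of demographic and clinical characteristics, which suggests a narrower intention. But the protocol gives no narrower list and its rule says all variables. A statistical analysis plan, not at hand, could restrict the set, but it would then depart from a rule the protocol has fixed rather than fill a gap.

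**The objective does not depend on this model.** This stands. Section 4.3.2 describes the sixth outcome as a comparison of control status across demographic groups, and the unadjusted tests deliver that. A reader might infer that the secondary objective cannot be answered at all; the document does not support that.

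**No ROC analysis is planned for this model.** This also stands. The ROC curves and Hosmer-Lemeshow test in section 9.3.3 belong to the frequent-exacerbations model. The AUC values above measure circularity; they do not predict a reported result.

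**The extreme result is conditional.** Correct. An AUC of exactly 1.00, and no variation left for other variables to explain, are certain only when both derived classes enter. With raw items the effect is displacement, and its size here rests on assumed data.

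**Components may be worth studying.** Section 2.3 mentions refining the tool, and knowing which components drive classification bears on that. A separate descriptive analysis serves that purpose better than a model that mixes components with correlates.

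**An analyst would notice.** Complete separation would be visible at fitting. Displacement by raw items would be less so, and exclusions chosen after seeing the fit would be data-driven.

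**Conclusion.** The point holds for the adjusted model. As written, section 9.3.4 offers the model the definition of its own outcome. With the impact and stability classes both in, separation is complete and maximum-likelihood estimates do not exist; this needs no assumption beyond the definition and the reading that the univariate comparisons cover the 9.3.1 variables. With only raw items, the exacerbation count alone lacks a finite coefficient under Tables 2 and 3, and the defining items tend to crowd out other characteristics. The drop for age from 71 to 2 runs in 100, and for FEV1 from 100 to 1, illustrates the direction and is not an estimate for this study.

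It would go too far to say that the model can only ever return components of the definition, or that the objective is lost. The consequence is confined to one model for one secondary objective. The primary outcome, the sample size and data collection are untouched. It should still be corrected, because a stated rule gives a misleading analysis and the repair is simple.

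**What to change.** Amend section 9.3.4 as follows.

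- **Candidates:** only baseline variables outside the control definition, for example age, sex, BMI, occupation, smoking, comorbidities, lung function, and medication or guideline-adequate treatment.
- **Excluded by name:** mMRC, sputum, walking time, rescue use, CAT, CCQ and their changes, exacerbations in the 3-month stability window, and the impact, stability and control classes. Rescue use is not in the 9.3.1 list, but naming it prevents it entering by another route.
- **Severity:** do not offer the BODE/BODEx score as a candidate. It contains dyspnea, and the severity class sets the cut-offs for control. Use the class as a fixed covariate or stratum, and note its overlap with BMI, FEV1 and prior exacerbations when reading those coefficients.
- **Components:** place any examination of which components drive the classification in a separate descriptive analysis.

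The unadjusted comparisons can stay as they are. The cost is a change of wording, carried into the statistical analysis plan if one exists. The variables named as candidates are in the 9.3.1 list or, for treatment adequacy, can be derived from the medication review in section 4.4.1.3. No additional data are needed.
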